16.3. Exploratory Efficacy

The exploratory endpoints include:

- Change in peak FEV₁ from Day 1 to Week 4
- Change in average AUC_{0-12h} FEV₁ from Day 1 to Week 4

Document: ...\\Verona_Pharma\\RPL554\\BZA48916\\Biostatistics\\Documentation\\SAP\\Verona CO-205 SAP v1.0

Author: [REDACTED] Version Number: V1.0

Version Date: 05DEC2019

Template No.: CS_TP_BS016 Revision 5

Reference: CS_WI_BS005

Effective Date: 01Apr2018

- Change from baseline in IC on Day 1 and at Week 4
- Change from baseline in the CAT questionnaire at Weeks 2 and 4
- Change from baseline (i.e. mean over the last 7 days of run-in) to the mean weekly values over Weeks 1 to 4 in morning symptoms
- Change from baseline (i.e. mean over the last 7 days of run-in) to the mean weekly values over Weeks 1 to 4 in morning activity limitations
- Proportion of patients with an improvement from baseline in CAT total score of 4 or more

16.3.1. Exploratory Efficacy Variables & Derivations

Peak FEV₁ is defined in Section 16.2.1.1.1. AUC_{0-T} will be derived as detailed in Section 16.2.1.1.2.

16.3.1.1. *DIARY DATA*

16.3.1.1.1. MORNING SYMPTOMS

Morning symptoms are scored based on the overall COPD symptom severity in the early morning before the first dose of COPD treatment. COPD symptoms include: cough, wheezing, shortness of breath, tightness in chest, chest congestion, difficulty bringing up phlegm. Patients will be asked to rate their symptoms between 0 to 4, 0="no symptoms" and 4="severe symptoms".

Weekly means are calculated as per method detailed in section 16.2.1.2.1.

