
(j) Pre-dose samples are for assay of tiotropium steady state exposure prior to and following 14 days of treatment with RPL554. PK samples from Visit 4 will also be used for assay pf RPL554 concentrations
 
(k) Study medication is to be dosed following administration of tiotropium
 
(l) At Visit 2, study medication is to be administered twice; first, just after randomization and again 12 hours later once all assessments are complete
								

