At Visit 1 an e-diary will be dispensed to the patients continuing in the study, who will use it twice daily in the morning and at bedtime. In addition to assessing use of tiotriopium, study medication and rescue use, the e-diary will collect symptom and activity information.

In the morning, patients will be prompted to answer the following questions:

- **Please rate your overall COPD symptom severity** in the early morning before your first dose of any COPD treatment. COPD symptoms include any of the following: cough,

- wheezing, shortness of breath, tightness in chest, chest congestion, difficulty bringing up phlegm.
- Rate your symptoms on a scale of 0 to 4: 0= no symptoms and 4= very severe symptoms
- **Please rate your early morning activity limitation** due to COPD symptoms before your first dose of any COPD medication.
 - Rate your ability to perform your daily activities in the morning upon awakening such as showering, making breakfast, dressing, etc.) on a scale of 0 to 4: 0= I do not have any difficulty in performing) to 4= I have great difficulty in performing.

In the evening, symptoms will be assessed using the E-RS™:COPD scale (EXACT-PRO® Initiative website, 2018). E-RS™:COPD uses the 11 respiratory symptom questions in the EXACT-PRO® instrument. Three subscales are used to assess breathlessness, cough/sputum and chest symptoms. The E-RS™:COPD has a scoring range of 0 to 40.

At Screening (Visit 1), study staff will train the patients on use of the e-diary as follows:

- Have patients log into the device using a password and read and answer all of the 14 questions to ensure comprehension
- Instruct patients to reflect on their day and answer the questions based on how they felt over the day
- Remind patients there are no right or wrong answers
- Remind patients that all 14 items are to be answered daily

7.2.3 *St. George's Respiratory Questionnaire – COPD specific (SGRQ-C)*

Patients will be asked to complete the SGRQ-C while they are at the study site at Visits 2, 4 and 6. The SRGQ-C is designed to measure impact on overall health, daily life, and perceived well-being in patients with COPD (Meguro et al, 2007). It is a revised version of the original SGRQ (Jones et al, 1991) in that it is intended only for COPD patients, is shorter in length and does not specify a recall period.

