Total and subdomain scores are derived weekly as the mean over total number of days between previous visit (inclusive) and the following visit, using only days where data was recorded. For the last visit, when patient completes the study the derivation will use days between previous visit (inclusive) and the following/last visit (inclusive). Baseline is the mean over the 7 days prior to the first intake of study treatment, using only days where data was recorded. If less than 4 days of data are available for the week, the weekly mean is set to missing, e.g. if data is entered for less than 4 days between Visits 2 and 3 then no result will be presented for Week 1. Furthermore, all questions need to be answered to be evaluable for that day.

If a patient discontinued then use treatment study end date, as the date of their last expected visit.

The EXACT-PRO total score will be calculated by first summing all raw scores and then looking up the corresponding EXACT-PRO total score in the table described in the Appendix 5.

E-RS subdomain score is calculated as the sum from the relevant questions.

16.2.1.2.2. *SGRQ-C*

St. George's Respiratory Questionnaire – COPD specific (SGRQ-C) is a questionnaire consisting of 14 questions, split into two parts. Part 1 consists of the first 7 questions and is related to the Symptoms subdomain. The remaining 7 questions are in Part 2, which are related to the Activity and Impacts subdomains. Each possible answer to each question has a weight assigned described in the Appendix 6.

Document: ...\\Verona_Pharma\\RPL554\\BZA48916\\Biostatistics\\Documentation\\SAP\\Verona CO-205 SAP v1.0

Author:  Version Number: V1.0

Version Date: 05DEC2019

Template No.: CS_TP_BS016 Revision 5

Reference: CS_WI_BS005

Effective Date: 01Apr2018

Calculating the score

Subdomains:

- Symptoms – items 1 to 7
- Activity – items 9 and 12
- Impacts – items 8, 10, 11, 13 and 14

The score for each component is calculated separately by dividing the summed weights by the maximum possible weight for that component and expressing the result as a percentage. A positive component has a non-zero response. It is not possible to have missing items in the questionnaire, as the data is collected in the e-diary which doesn't allow patients to skip between items.

$$Score = 100 * \frac{\text{Sum of weights from all positive items in that component}}{\text{Sum of maximum weights for all items in that component}}$$

The total score is calculated similarly

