16.3.1.1.2. MORNING ACTIVITY LIMITATIONS

Morning activity limitations are scored based on the activity limitations in the early morning before the first dose of COPD treatment. Morning activities will include: showering, making breakfast, dressing, etc. Patients will be asked to rate their activity limitations between 0 to 4, 0="I do not have any difficulty in performing" and 4="I have great difficulty in performing".

Weekly means are calculated as per method detailed in section 16.2.1.2.1.

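### The Week 1 means of morning symptoms and morning activity limitation include the Day 1 morning score, which precedes the first study dose, so the Week 1 effect is diluted by about one seventh

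*SAP*

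**What the plan says.** SAP 16.3.1.1.1 describes the first item: "Morning symptoms are scored based on the overall COPD symptom severity in the early morning before the first dose of COPD treatment". SAP 16.3.1.1.2 describes the second in parallel terms: "Morning activity limitations are scored based on the activity limitations in the early morning before the first dose of COPD treatment". Both sections then hand the averaging over to the E-RS section with the same sentence: "Weekly means are calculated as per method detailed in section 16.2.1.2.1".

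The rule in SAP 16.2.1.2.1 is that scores are "derived weekly as the mean over total number of days between previous visit (inclusive) and the following visit". The closing visit is counted only for the last week of a patient who completes. A weekly mean needs at least four recorded days. Baseline is the mean over the seven days before the first intake of study treatment.

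The Protocol fixes the timing:

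- Section 7.2.2 has the diary dispensed at Visit 1 to patients "who will use it twice daily in the morning and at bedtime". The morning symptom question asks for severity "in the early morning before your first dose of any COPD treatment", and the activity question has the same reference time. The E-RS is completed in the evening.
- A footnote to Table 4 in Section 6 sets the first study dose: "At Visit 2, study medication is to be administered twice; first, just after randomization". Section 3.1 has patients withhold study treatments, including tiotropium, before visits.

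**The concern.** One calendar window is applied to two kinds of diary entry that fall on opposite sides of the first dose. On Day 1 the evening E-RS is a post-dose observation and belongs in Week 1. The morning ratings of that same date describe the hours before randomised treatment began, so they are baseline observations. Averaging them into Week 1 adds a value whose expected difference between arms is zero, and that pulls every Week 1 contrast towards zero, both against placebo and between doses.

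SAP 16.3.2 sends these endpoints to the repeated-measures model of 16.1.2, which has a treatment-by-visit interaction. Week 1 therefore gets its own estimate. The practical risk is an understated early effect. A constant true effect would also appear to grow between Week 1 and Week 2 purely because of the window.

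**Working it through.** The documents state no figure for this point, so there is none to reproduce.

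**Which days fall in Week 1**

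1. SAP 16.2.1.2.1 includes the opening visit. It includes the closing visit only for the final week. SAP 16.2.1.4 uses the same window for rescue medication and says there that Week 1 runs from Visit 2 to Visit 3.
2. Visit 2 is Day 1. Protocol Section 6 spaces the treatment visits 7 days apart, plus or minus 1. Week 1 is therefore Days 1 to 7 nominally, with 6 to 8 days possible.
3. The diary has been in use since Visit 1, so a Day 1 morning entry is expected. It precedes the in-clinic dose.
4. No other rule removes it. The SAP 6.4 windows that start Week 1 after Day 1 apply to the End of Study visit of patients who discontinue, not to weekly diary means.

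**Size of the dilution**

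Let k be the number of recorded days in the Week 1 mean, Day 1 among them, and d a constant true difference on each post-dose morning. The Day 1 difference has expectation 0, so

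expected Week 1 difference = [0 + (k − 1)·d] / k = d·(k − 1)/k, and the share lost is 1/k.

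| Recorded days k | Kept | Lost |
|---|---|---|
| 8 | 7/8 = 87.5% | 12.5% |
| 7 (nominal) | 6/7 = 85.7% | 14.3% |
| 6 | 5/6 = 83.3% | 16.7% |
| 4 (minimum) | 3/4 = 75.0% | 25.0% |
| Day 1 not recorded | 100% | 0% |

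Illustration (the 0.20 is an assumption, not a document figure): a true difference of 0.20 points would be estimated as 0.20 × 6/7 = 0.171.

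Apparent growth from Week 1 to Week 2 under a constant effect: 1 / (6/7) = 1.167, about 17%.

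**If the effect is not constant**

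Assume the effect rises linearly, reaching full size d on the seventh post-dose morning (Day 8).

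- Mean over Days 1 to 7: (0 + 1 + … + 6)/7 ÷ 7 = 3/7 = 0.429·d
- Mean over Days 2 to 7: (1 + … + 6)/7 ÷ 6 = 3/6 = 0.500·d
- Mean over Days 2 to 8: (1 + … + 7)/7 ÷ 7 = 4/7 = 0.571·d

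The present window keeps 0.429/0.500 = 85.7% of the Day 2–7 mean and 0.429/0.571 = 75% of the Day 2–8 mean.

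**Later weeks**

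Weeks 2 to 4 contain only post-dose mornings, so nothing is lost there by this mechanism. The Visit 3 morning rating (Day 8, before that day's dose) reflects Week 1 treatment but is counted in Week 2. The morning windows therefore sit one day early throughout.

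**The case against.** The strongest reply is about reach. Both items are exploratory, only the first of four weeks is touched, and the same rule applies in every arm, so the bias is towards no effect. An unweighted average of the four weekly differences, which the SAP does not name as a contrast, would lose only (1/7)/4 = 3.6% under a constant effect. All of this stands, and it makes the point a minor one.

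A second reply is that the window may be a deliberate common convention for all diary data, since SAP 16.2.1.4 writes it separately for rescue use. The documents do not say why it was chosen. The reason does not matter, because a common window still puts a pre-dose rating in a post-baseline mean for these two items.

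A third reply is that the baseline boundary is unclear. SAP 16.2.1.2.1 anchors baseline to first intake, while the endpoint lists refer to the end of run-in. The Day 1 morning rating could be read as belonging to baseline, to Week 1, or to both. The ambiguity is real, but it does not rescue the rule. The rating precedes first intake, so placing it in baseline fits the SAP's own wording. If it were counted in both places, the expected difference between arms would still be diluted by 1/k, because randomised arms have the same expected baseline.

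Finally, one seventh assumes a full diary and a roughly constant effect from the first post-dose morning. That is correct, and the range including zero must go with the figure.

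**Conclusion.** The concern holds. Followed as written, the SAP averages a pre-treatment morning rating into the Week 1 mean of both morning endpoints and biases the Week 1 treatment differences towards zero. The loss is 14.3% for a full seven-day week with a roughly constant effect, and 12.5% to 16.7% within the visit windows. It reaches 25% when only four days including Day 1 are recorded, and is nil for a patient with no Day 1 morning entry. The documents give no expected effect or standard deviation for these items, so the clinical weight of the loss cannot be judged from them. The point is confined to Week 1 of two exploratory endpoints and is a low-priority correction.

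**What to change.** Replace the cross-reference in SAP 16.3.1.1.1 and 16.3.1.1.2 with a rule specific to the morning items: each week runs from the day after the previous visit through the morning of the next visit, inclusive. At nominal spacing this gives Days 2–8, 9–15, 16–22 and 23–29. Each week then has seven mornings, all after the first dose, and Week 1 loses no days. The present rule gives seven mornings in Weeks 1 to 3 and eight in Week 4.

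State in the same place that the Day 1 morning rating belongs to baseline, so that the seven baseline mornings end on Day 1 (Day −6 to Day −1 plus Day 1, as the SAP has no Day 0). Align the run-in wording of the endpoint lists with this. The four-day minimum and the evening E-RS window can stay as they are.

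The cost is one sentence for the weekly window, a short addition for the baseline boundary, and a small programming change. No new data are needed. If the SAP can no longer be amended, Protocol 9.1 allows the departure to be described and justified in the clinical study report.

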16.3.1.1.2. MORNING ACTIVITY LIMITATIONS

Morning activity limitations are scored based on the activity limitations in the early morning before the first dose of COPD treatment. Morning activities will include: showering, making breakfast, dressing, etc. Patients will be asked to rate their activity limitations between 0 to 4, 0="I do not have any difficulty in performing" and 4="I have great difficulty in performing".

Weekly means are calculated as per method detailed in section 16.2.1.2.1.

16.3.2. Analysis of Exploratory Efficacy Variables

Peak FEV₁, CAT scores, morning symptoms and morning activity limitations will be analysed using an MMRM approach, as described in Section 16.1.2.

Due to AUC_{0-12h} FEV₁ only being derived for Day 1 and Week 4, an ANCOVA analysis of the change from baseline will be performed with fixed effects for treatment and actual reversibility strata, and baseline as a covariate. Each measurement will be graded based on the quality of the measurement. Grades "Acceptable" and "Borderline Acceptable" will be used in the analyses, as

Document: ...\\Verona_Pharma\\RPL554\\BZA48916\\Biostatistics\\Documentation\\SAP\\Verona CO-205 SAP v1.0

Author:  Version Number: V1.0

Version Date: 05DEC2019

Template No.: CS_TP_BS016 Revision 5

Reference: CS_WI_BS005

Effective Date: 01Apr2018

these will indicate usable measurements. Grade “Unacceptable” will not be used in the analysis, as the measurement will be identified as poor quality.

Total score data will be used for the CAT questionnaire analysis.

An analysis of the proportion of patients with an improvement from baseline in CAT total score of 4 or more will be summarised by visit and treatment group and analysed using logistic regression. The model will include randomised treatment groups and actual reversibility strata as factors. Patients with a missing response will be assumed to be a non-responder. Also, total score and subdomain scores will be listed. A plot of the least square means change from baseline in total score over time will be presented (based on the MMRM analysis).

Due to IC only being collected on Day 1 and at Week 4 for two timepoints 30 minutes pre-dose and 2 hours post-dose, an ANCOVA analysis of the change from baseline (Day 1, 30 minutes pre-dose) to remaining 3 timepoints will be performed with fixed effects for treatment and actual reversibility strata, and baseline as a covariate. Each measurement will be graded based on the quality of the measurement. Grades “Acceptable” and “Borderline Acceptable” will be used in the analyses, as these will indicate usable measurements. Grade “Unacceptable” will not be used in the analysis, as the measurement will be identified as poor quality.

16.4. Missing Data Methods for Efficacy Variables

Data for calculation of average (AUC) effects for FEV₁ will be imputed if the pre-dose is not missing. This will be done using the following method:

- ‘bounded’ missing data will use interpolation through the trapezoidal method described in section 16.2.1.1.2,
- ‘unbounded’ missing data will not be imputed
 - If last measurement is missing, then the AUC will be calculated up to the point where data is not missing, however if two or more last measurements will be missing, then the AUC will be set to missing.
 - If first measurement is missing, the AUC will not be calculated and set to missing.

For the analysis of responder on SGRQ-C and CAT missing responses will be treated as indicating non-responders in the analysis.

All other missing data, including for when pre-dose is missing, will not be imputed.

For the sensitivity and interim analysis missing data will be imputed using LOCF method. In cases where patient discontinues early and has spirometry data reported at the EOS visit, the following strategy explained below will be used.

1. Check the visit day at which EOS visit was performed against the following window for

Document: ...\\Verona_Pharma\\RPL554\\BZA48916\\Biostatistics\\Documentation\\SAP\\Verona CO-205 SAP v1.0

Author: [REDACTED] Version Number: V1.0

Version Date: 05DEC2019

Template No.: CS_TP_BS016 Revision 5

Reference: CS_WI_BS005

Effective Date: 01Apr2018

each visit:

- a. Day 1 = Day 1
- b. Week 1 = after day 1 and up to and including day 9
- c. Week 2 = after day 9 and up to and including day 16
- d. Week 3 = after day 16 and up to and including day 23
- e. Week 4 = after day 23 and up to and including day 30

2. Set the value for the corresponding visit, and any subsequent visits, to be the value from EOS. If the corresponding visit has a measurement already, then the next available visit must be used for EOS.
3. If there are missing values before the EOS corresponding visit, we would impute using LOCF in the usual manner.

In the case where patient discontinues early and did not have spirometry data recorded at the EOS visit, or cases of missing data for patients who did not discontinue early, LOCF will be applied in the usual manner.

16.5. Sensitivity analysis for Efficacy Variables

Sensitivity analyses will be done for the primary endpoint (change from baseline FEV₁ to peak FEV₁ at Week 4) and for key secondary endpoints (change from baseline FEV₁ to average AUC_{0-12h} FEV₁ at Week 4, and change from baseline in total E-RSTM:COPD score at Week 4). An ANCOVA approach will be used to compare treatment groups, with fixed factors for treatment and actual reversibility strata, and the baseline result as a covariate. RPL554 treatments will be compared to placebo and to each other, as described in Section 16.1.2.

As a sensitivity analysis, the primary analysis (i.e. MMRM) of the efficacy endpoints described above will be repeated on the PPS set.

Furthermore, an analysis of the proportion of patients with an improvement from baseline in SGRQ-C total score of 4 or more will be summarised by visit and treatment group and analysed using logistic regression. The model will include randomised treatment groups and actual reversibility strata as factors. Patients with a missing response will be handled according to last known responder status (LOCF).

Any missing data post-baseline will be imputed using the LOCF method described in Section 16.4.

Sensitivity analysis, with respect to impact of rescue use during clinic visits, will only be performed if at least one patient is excluded from this analysis due to taking rescue medication within 6 hours of spirometry test. Patient can only be excluded from the analysis if enough of the spirometry tests are affected for the function tests not being able to be calculated, i.e. if first

Document: ...\\Verona_Pharma\\RPL554\\BZA48916\\Biostatistics\\Documentation\\SAP\\Verona CO-205 SAP v1.0

Author: [REDACTED] Version Number: V1.0

Version Date: 05DEC2019

Template No.: CS_TP_BS016 Revision 5

Reference: CS_WI_BS005

Effective Date: 01Apr2018

FEV₁ measurement is affected by the rescue medication then AUC cannot be calculated for that visit.

This additional sensitivity analysis, taking into account rescue medication, will be performed for a secondary endpoint, change from baseline FEV₁ to average AUC_{0-12h} FEV₁ at Week 4.

16.6. Interim Analysis

To check the assumptions in the sample size calculation, as detailed in Section 9.5 of the study protocol, a blinded sample size-re-estimation is planned after 125 patients who have been randomized, have collected sufficient data after intake of study treatment to compute any of the FEV₁ parameters and either completed the study or had early termination. Analyses will be based on data that is as clean as possible at the time of the data cut-off.

Two different models will be fitted to the data and both will estimate blinded standard deviation which will be compared to the standard deviation assumption of 200 mL included in the original sample size calculation. Using each of these blinded estimates of the standard deviation, the original sample size calculation, based on a two-sample t-test, will be repeated for each of the following scenarios.

- Calculation 1 – unknown sample size (per treatment group), known detectable treatment difference (93 mL) and power (80%)
- Calculation 2 – unknown power (%), known detectable treatment difference (93 mL) and sample size (73 per treatment group)
- Calculation 3 – Unknown detectable treatment difference (mL), known power (80%) and sample size (73 per treatment group)

The ANCOVA analysis will be performed on the following endpoints. The MMRM analysis will be performed for the first endpoint only:

- Change from baseline FEV₁ to peak FEV₁ at Visit 6
- Change from baseline FEV₁ to average AUC_{0-3h} FEV₁ at Visit 6
- Change from baseline FEV₁ to average AUC_{0-12h} FEV₁ at Visit 6
- Change from baseline FEV₁ to morning trough FEV₁ at Visit 6

